Appendix I: Data Processing Annex (DPA)

Definitions:

- “Protocol” means the document entitled Naltrexon/bupropion with or without very low calorie ketogenic diet for weight regain after bariatric surgery containing the details of the academic Study as developed by the Sponsor and approved by the relevant Ethics Committee.
- “Sponsor” means University Hospitals Leuven (UZ Leuven).
- Participating site acts as a data processor as defined under article 4, 8) of the Regulation (EU) 2016/679 (“Data Processor”) for the Sponsor who acts as data controller as defined under article 4, 7) of the Regulation (EU) 2016/679 (“Data Controller”).
- “Applicable Law” means any applicable data protection or privacy laws, including:
 - b) the Regulation (EU) 2016/679 also referred as the General Data Protection Regulation (“GDPR”);
 - c) other applicable laws that are similar or equivalent to or that are intended to or implement the laws that are identified in (a) of this definition;
- “Personal Data” means any information relating to an identified or identifiable natural person (“Data Participant”), including without limitation pseudonymized information, as defined in Applicable Law and described in the Protocol.

Rights and obligations:

1. The Data Processor is instructed to process the Personal Data for the term of the Study and only for the purposes of providing the data processing tasks set out in the Protocol. The Data Processor may not process or use Personal Data for any purpose other than a Data Participant’s medical records, or other than provided in the instructions of the Study protocol, including with regard to transfers of personal data to a third country or an international organization, unless the Data Processor is required to do so according to Union or Member State law.
2. Data Processor shall at all times maintain a record of processing of Personal Data in accordance with Applicable Law and if the Data Processor considers an instruction from the Data Controller to be in violation of the Applicable Law, the Data Processor shall promptly inform the Data Controller in writing about this.
3. The Data Processor must ensure that persons authorized to process the Personal Data have committed themselves to confidentiality or are under an appropriate statutory obligation of confidentiality.
4. The Data Processor shall implement appropriate technical and organizational measures to prevent that the Personal Data processed is:
 - (i) accidentally or unlawfully destroyed, lost or altered,
 - (ii) disclosed or made available without authorization, or
 - (iii) otherwise processed in violation of Applicable Law.
5. The appropriate technical and organizational security measures must be determined with due regard for:
 - (i) the current state of the art,
 - (ii) the cost of their implementation, and
 - (iii) the nature, scope, context and purposes of processing as well as the risk of varying likelihood and severity for the rights and freedoms of natural persons.

6. Taking into account the nature of the processing, the Data Processor shall assist the Data Controller, by means of appropriate technical and organizational measures, insofar as this is possible, in fulfilling its obligation to respond to requests from Data Participants pursuant to laws and regulations in the area of privacy and data protection (such as, the right of access, the right to rectification, the right to erasure, the right to restrict the processing, the right to data portability and the right to object)
7. The Data Processor shall upon request provide the Data Controller with sufficient information to enable the Data Controller to ensure that the Data Processor's obligations under this DPA are complied with, including ensuring that the appropriate technical and organizational security measures have been implemented.
8. The Data Controller is entitled to appoint at its own cost an independent expert, reasonably acceptable to the Data Processor, who shall have access to the Data Processor's data processing facilities and receive the necessary information for the sole purpose of auditing whether the Data Processor has implemented and maintained said technical and organizational security measures. The expert shall upon the Data Processor's request sign a non-disclosure agreement provided by the Data Processor, and treat all information obtained or received from the Data Processor confidentially, and may only pass on, after conferral with the Data Processor, the findings as described under 10) (ii) below to the Data Controller.
9. The Data Processor must give authorities who by Union or Member State law have a right to enter the Data Controller's or the Data Controller's processors' facilities, or representatives of the authorities, access to the Data Processor's physical facilities against proper proof of identity and mandate, during normal business hours and upon reasonable prior written notice.
10. The Data Processor must without undue delay in writing notify the Data Controller about:
 - (i) any request for disclosure of Personal Data processed under the Protocol by authorities, unless expressly prohibited under Union or Member State law,
 - (ii) any finding of (a) breach of security that results in accidental or unlawful destruction, loss, alteration, unauthorized disclosure of, or access to, Personal Data transmitted, stored or otherwise processed by the Data Processor under the Protocol, or (b) other failure to comply with the Data Processor's obligations, or
 - (iii) any request for access to the Personal Data (with the exception of medical records for which the Data Processor is considered data controller) received directly from the Data Participants or from third parties.
11. Such a notification from the Data Processor to the Data Controller with regard to a breach of security as meant in 10) (ii)(a) above will contain at least the following information:
 - (i) the nature of the Personal Data breach, stating the categories and (by approximation) the number of Data Participants concerned, and stating the categories and (by approximation) the number of the personal data registers affected (datasets);
 - (ii) the likely consequences of the Personal Data breach;
 - (iii) a proposal for measures to be taken to address the Personal Data breach, including (where appropriate) measures to mitigate any possible adverse effects of such breach.
12. The Data Processor shall document (and shall keep such documentation available for the Data Controller) any Personal Data breaches, including the facts related to the Personal Data breach, its effects and the corrective measures taken. After consulting with the Data Controller, the Data Processor shall take any measures needed to limit the (possible) adverse effects of Personal Data breaches (unless such consultation cannot be awaited due to the nature of the Personal Data breach).
13. The Data Processor must promptly and reasonably assist the Data Controller (with the handling of (a) responses to any breach of security as described in 10) (ii) above and (b) any requests from Data Participants under Chapter III of the GDPR, including requests for access, rectification, blocking or deletion. The Data Processor must also reasonably assist the Data Controller by

implementing appropriate technical and organizational measures for the fulfilment of the Data Controller's obligation to respond to such requests.

14. The Data Processor must reasonably assist the Data Controller with meeting the other obligations that may be incumbent on the Data Controller according to Union or Member State law where the assistance of the Data Processor is implied, and where the assistance of the Data Processor is necessary for the Data Controller to comply with its obligations. This includes, but is not limited to, at the request to provide the Data Controller with all necessary information about an incident under 10) (ii), and all necessary information for an impact assessment in accordance with Article 35 and Article 36 of the GDPR.

[figure not shown]
Subprocessor:

15. The Data Processor may only engage a subprocessor, with prior specific or general written consent from the Data Controller. The Data Processor undertakes to inform the Data Controller of any intended changes concerning the addition or replacement of a subprocessor by providing a reasonable prior written notice to the Data Controller. The Data Controller may reasonably and in a duly substantiated manner object to the use of a subprocessor. The Data Processor must inform the Data Controller in writing of the discontinued use of a subprocessor.
16. Prior to the engagement of a subprocessor, the Data Processor shall conclude a written agreement with the subprocessor, in which at least the same data protection obligations as set out in this DPA shall be imposed on the subprocessor, including obligations to implement appropriate technical and organizational measures and to ensure that the transfer of Personal Data is done in such a manner that the processing will meet the requirements of the Applicable Law.
17. The Data Controller has the right to receive a copy of the relevant provisions of Data Processor's agreement with the subprocessor related to data protection obligations. The Data Processor shall remain fully liable to the Data Controller for the performance of the subprocessor obligations under this DPA. The fact that the Data Controller has given consent to the Data Processor's use of a subprocessor is without prejudice for the Data Processor's duty to comply with this DPA.

Appendix 2: [Pro Well VLCKD protocol]

- BMI 27+ program: 10 weeks
 - 4 weeks VLCKD strict phase: 800 kcal/day (<50g carbs, >100g proteins, vegetables with a low carb content)
 - 3 x 2 weeks of progressive increase of daily kcal: 1000 kcal, 1200 kcal (W) / 1400 kcal (M), 1500 kcal (W) / 1800 kcal (M) based on Mediterranean diet
 - Coaching minutes: 2 hours 15 minutes

Intake	30 minutes	Explanation VLCKD & App
Follow-up 1: after 3 weeks	15 minutes	Follow-up
Follow-up 2: after 4 weeks	15 minutes	Explanation 1000 kcal meal plan
Follow-up 3: after 6 weeks	15 minutes	Explanation 1200/1400 kcal meal plan
Follow-up 4: after 8 weeks	15 minutes	Explanation 1400/1800 kcal meal plan
Outtake after 10 weeks	15 minutes	Progress & Reflection

Appendix 3: [Pro Well Lifestyle protocol]

- **Lifestyle e-learning program :**
- **30 minutes 1-on-1 coaching and regular personal follow-up by telephone (if possible regular videocall Whatsapp/FaceTime)**
- **3 modules including 12 educational presentations**
- **12 practical tasks to apply in daily life**

[figure not shown]
- **Lifestyle e-learning program in addition to Naltrexon/bupropion**

Lifestyle coaching I: at the start	15 minutes	Intake: overview e-learning modules and tasks
Lifestyle coaching I: month 1 & 2	e-learning	Module : nutrition & 4 tasks about nutrition
Lifestyle coaching I: after 1 month	Telephone	Follow-up
Lifestyle coaching I: after 2 months	Telephone	Follow-up
Lifestyle coaching I: month 3 & 4	e-learning	Module : physical exercise & 4 tasks
Lifestyle coaching I: after starting module 2	15 minutes	Introducing a personal exercise program
Lifestyle coaching I: after 3 months	Telephone	Follow-up
Lifestyle coaching I: after 4 months	Telephone	Follow-up
Lifestyle coaching I: month 5 & 6	e-learning	Module : Lifestyle topics sleep, stress management, relaxation and focus
Lifestyle coaching I: after month 5	Telephone	Follow-up
Lifestyle coaching I: at the end of month 6	Telephone	Outtake questionnaire: reflection & future goals

- **Lifestyle e-learning program as a follow-up after 10 weeks BMI 27+ starting after 3 months**

Lifestyle coaching I: after 3 months	15 minutes	Intake: overview e-learning modules and tasks
Lifestyle coaching I: month 4	e-learning	Module : nutrition & 4 tasks about nutrition
Lifestyle coaching I: halfway month 4	Telephone	Follow-up
Lifestyle coaching I: at the end of month 4	Telephone	Follow-up
Lifestyle coaching I: month 5	e-learning	Module : physical exercise & 4 tasks
Lifestyle coaching I: after starting module 2	15 minutes	Introducing a personal exercise program
Lifestyle coaching I: halfway month 5	Telephone	Follow-up
Lifestyle coaching I: at the end of month 5	Telephone	Follow-up
Lifestyle coaching I: month 6	e-learning	Module : Lifestyle topics sleep, stress management, relaxation and focus
Lifestyle coaching I: halfway month 6	Telephone	Follow-up
Lifestyle coaching I: at the end of month 6	Telephone	Outtake questionnaire: reflection & future goals

Lifestyle e-learning program in addition to Naltrexon/bupropion

BMI 27+ and Lifestyle Coaching

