Procedures/assessments	Phase 0: Screening and randomization		Phase 1: Lifestyle + NB with vs without VLCKD							Phase 2: Lifestyle + NB (all participants)				Follow-up (all participants)		
	Screening (In-clinic)	Randomization (in-clinic)	Remote	Remote	Remote	Remote	Remote	Remote	In-clinic (study specific)	Remote	Remote	In-clinic (Routine)	Remote	Remote	In-clinic (study specific)	In-clinic (routine)
Visit	V1	V2	V3	V4	V5	V6	V7	V8	V9	V10	V11	V12	V13	V14	V15	V16
Timing of visits (weeks)		Start	Start	W3	W4	W6	W8	W10	W10	W12	W16	W16	W20	W26	W26	W52
Visit window (days)									±30			±30			±30	±30
Lifestyle program			X		X		X			X	X		X	X		
Naltrexone/bupropion (NB)		X							X			X			X	X
VLCKD			(X) ¹	(X) ¹	(X) ¹	(X) ¹	(X) ¹	(X) ¹								
Screening assessments and randomization																
Informed consent	X ²															
Inclusion/exclusion criteria	X	X														
Randomization		X														
Anthropometric data (height, weight, waist circumference)		X							X			X			X	X

Clinical examination (Blood pressure, heart and lung auscultation, abdominal palpitation and percussion)		X							X			X				X	X
Laboratory tests																	
Fasting glucose		X							X			X				X	X
Hemoglobin A1c		X										X					X
Lipids: LDL-cholesterol, HDL-cholesterol, triglycerides		X							X			X				X	X
Liver test: AST, ALT, gamma-GT, alkaline phosphatase, total bilirubin, albumin		X										X					X
Kidney function: creatinine, eGFR		X										X					X
Thyroid function: TSH, free T4		X										X					X
Uric acid		X										X					X
Questionnaires																	
The PsyEndoAUDIT questionnaire ³		X							X			X				X	X
The PsyEndoCIDI questionnaire ³		X							X			X				X	X
The PsyEndoEDE questionnaire ³		X							X			X				X	X
The PsyEndoHADS questionnaire ³		X							X			X				X	X
Nederlandse vragenlijst voor eetgedrag ³		X							X			X				X	X
The ObesitasIPAQ questionnaire ³		X							X			X				X	X

The quality of life (SF-36) questionnaire ³		X							X				X			X	X
The outtake questionnaire															X		
Reason for discontinuation		X							X			X			X	X	
(Serious) Adverse event (S)(AE) assessment		X							X			X			X	X	

- Depending on randomization in either intervention (with VLCKD) or comparator group (without VLCKD).
- Informed Consent must be obtained prior to performing any other Trial-related procedures as part of the standard of care.
- See appendix 4 for the respective questionnaires.

I Background and Rationale

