Generally, there is a lack of published data on the effectiveness of pharmacotherapies for post-bariatric weight regain. Therefore, this trial aims to investigate a structured follow-up with lifestyle intervention combined whether or not with a VLCKD and supported by naltrexone/bupropion on the evolution of bodyweight in patients with weight regain post-bariatry. This multi-center, randomized clinical trial will compare the outcomes of two different groups. The patients in both groups need to undergo lifestyle changes in combination with the intake of naltrexone/bupropion, but the experimental group needs to follow a VLCKD on top of it for a period of 10 weeks.]

2 Study Design and Objectives

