2.4 Study design

This is a parallel multicentric longitudinal randomized controlled trial in which prospective data will be collected from the electronic health record. The inclusion and exclusion criteria will be checked and afterwards patients will be randomized to (unblinded) medication only or combination with VLCKD. Both groups include NB and lifestyle changes for 26 weeks but the patients belonging to the experimental group must follow a VLCKD in the first 10 weeks on top of it. Like the other group, the remaining 16 weeks will consist of NB combined with lifestyle interventions. Afterwards there is a follow-up extension of 26 weeks. See appendix 4 for detailed overview of clinical and biochemical parameters to be collected during the trial.

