2.5 Expected duration of the Study

[This trial will have a duration of 2 years in total. 1 year is taken into account to include the patients into the study according to the inclusion and exclusion criteria. Afterwards patients will be randomly inserted into the comparator arm (NB + lifestyle interventions) or experimental arm (NB + Lifestyle interventions + VLCKD). Both arms of the study design will be evaluated for 52 weeks. 26 weeks will consist of the treatment after which another 26 weeks will be used as a follow-up extension.]

The End of Study is defined as Last Patient Last Visit (LPLV). The CI shall notify the EC of the end of the Study. The CI will submit a final report with the results of the study, including any publications/abstracts, to the EC within 1 year of study termination.

The Sponsor or EC can decide to halt or prematurely terminate the Study when new information becomes available whereby the rights, safety and well-being of Study participants can no longer be assured, when the integrity of the Study has been compromised, or when the scientific value of the Study becomes obsolete and/or unjustifiable]

3 Study Population / Eligibility Criteria

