4.8 Lifestyle

Lifestyle support, excluding the VLCKD, is offered to both the experimental and comparator arms and is regarded as part of the standard care protocol. Consequently, both groups will both have a total of 11 contact sessions, during which 30 minutes will be allocated for individual coaching and routine personal follow-up via telephone. Additionally, there are three modules comprising 12 educational presentations and 12 practical tasks designed for application in everyday life. For a comprehensive schedule outlining specific time points, please refer to Appendix 3.

5 Assessment of Safety

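### Appendix 3 delays lifestyle coaching by 3 months after the VLCKD, whereas section 2.4 and the flowchart start it at week 0 in both arms

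*Protocol*

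**What the plan says.** The body of the protocol describes a pure add-on design.

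- Section 1 (last paragraph) gives both groups lifestyle changes and NB, and adds that "the experimental group needs to follow a VLCKD on top of it for a period of 10 weeks".
- Section 2.4: "Both groups include NB and lifestyle changes for 26 weeks". For the experimental arm after the diet: "Like the other group, the remaining 16 weeks will consist of NB combined with lifestyle interventions".
- The study flowchart heads weeks 0 to 10 "Phase 1: Lifestyle + NB with vs without VLCKD". Its lifestyle row is marked at the start and at weeks 4, 8, 12, 16, 20 and 26. The footnote on randomised arm is attached to the VLCKD row only.

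Section 4.8 offers the same lifestyle support to both arms and hands the timing to an appendix: "For a comprehensive schedule outlining specific time points, please refer to Appendix 3".

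Appendix 3 prints two schedules. The first accompanies NB, begins at the start and spreads three modules over months 1 to 6. The second is headed "Lifestyle e-learning program as a follow-up after 10 weeks BMI 27+ starting after 3 months". Its intake is at 3 months, and the same three modules are fitted into months 4, 5 and 6. Appendix 2 describes the VLCKD under the label "BMI 27+ program: 10 weeks".

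**The concern.** The experimental arm cannot both start lifestyle coaching at week 0 (section 2.4, flowchart) and start it after 3 months (Appendix 3, second schedule). Because section 4.8 names Appendix 3 as the source of the time points, staff could reasonably deliver the delayed schedule.

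In that case the arms differ in two respects: the VLCKD, and the start and pace of the lifestyle programme. Differences in weight loss at week 26 (primary) and at weeks 10 and 16 (secondary) would reflect both. The add-on question in sections 1 and 2.4 could not be answered from them. If some staff follow the flowchart and others Appendix 3, the intervention would also vary within the arm. No analysis can settle afterwards which programme was meant to be given.

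**Working it through.** **Which arm the second schedule belongs to.** Appendix 3 names no arm. Appendix 2 equates BMI 27+ with the 10-week VLCKD, which only the experimental arm receives. A lifestyle schedule that follows BMI 27+ therefore has no use in the comparator arm.

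**The plan's own count.** Section 4.8 gives 11 contact sessions in each group. Each Appendix 3 table has 11 rows: 3 e-learning blocks, 7 dated live contacts and 1 undated live contact (after module 2 begins). So 3 + 7 + 1 = 11, and the total reproduces for both schedules. The disagreement is about timing.

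**Dated live contacts, in months.**
- First schedule: 0, 1, 2, 3, 4, 5, 6.
- Second schedule: 3, 3.5, 4, 4.5, 5, 5.5, 6.

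**Conversion to weeks.** The protocol does not define a month, so two assumptions are shown.
- Calendar month, about 4.35 weeks: first schedule 0, 4.3, 8.7, 13.0, 17.4, 21.7, 26; second schedule 13.0, 15.2, 17.4, 19.6, 21.7, 23.9, 26.
- 4-week month with the last contact at week 26, as in the flowchart: first schedule 0, 4, 8, 12, 16, 20, 26; second schedule 12, 14, 16, 18, 20, 22, 26.

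The flowchart's seven lifestyle marks match the first schedule exactly on the 4-week month. The second schedule's calls at weeks 14, 18 and 22 have no flowchart visit, so the flowchart cannot describe an arm that follows it.

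**Delivery if Appendix 3 is followed.**

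| By week | Quantity | Comparator | VLCKD arm |
|---|---|---|---|
| 10 | dated contacts | 3 | 0 |
| 10 | weeks on programme | 10 | 0 |
| 10 | nutrition module | finished | not started |
| 16 | dated contacts, calendar month | 4 | 2 |
| 16 | dated contacts, 4-week month | 5 | 3 |
| 16 | weeks on programme | 16 | 3–4 |
| 26 | dated contacts | 7 | 7 |
| 26 | modules | 3 | 3 |
| 26 | weeks on programme | 26 | 13–14 |

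Weeks on programme in the VLCKD arm are 16 − 13.0 = 3.0 or 16 − 12 = 4.0 at week 16, and 26 − 13.0 = 13.0 or 26 − 12 = 14.0 at week 26. The diet ends at week 10, so the interval to the lifestyle intake is 13.0 − 10 = 3.0 or 12 − 10 = 2.0 weeks. The VLCKD coaching sessions are part of the diet under either reading and are not counted.

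**Delivery if the flowchart is followed.** Both arms have 3 contacts before week 10 (V3, V5, V7), 5 by week 16 and 7 by week 26. The arms do not differ.

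**Sample size.** The stated 62 is not in dispute. With a difference of 12 − 6.75 = 5.25 points and a pooled SD of √((7.12² + 5.3²)/2) = 6.28, a t-test needs 24 evaluable per arm for 80% power. Then 24/0.8 = 30 per arm, or 60 in total, close to the protocol's figure.

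**The case against.** - **Appendix 3 does not assign its schedules to arms.** The heading of the first could fit both arms, since both take NB, and figures in that appendix are not visible in the text available. This stands in part: the documents do not show which schedule will be delivered. It does not remove the conflict, because the second schedule is in the current text and can only concern patients who had the VLCKD.
- **The VLCKD arm is not unsupported in weeks 0 to 10.** Appendix 2 gives it six coaching sessions (weeks 0, 3, 4, 6, 8 and 10). This is true, and the 3 versus 0 count should not be read as no contact. But those sessions cover the diet, and section 4.8 defines lifestyle support as separate from the VLCKD.
- **The interval after the diet is minor.** The flowchart's first lifestyle contact after week 10 is also at week 12, and 2–3 weeks is shorter than the comparator's monthly spacing. This stands. The difference that matters is that week 12 continues the programme in the flowchart but opens it in Appendix 3.
- **The objective in section 2.1 already compares packages.** It does, but section 1, section 2.4 and the flowchart present the VLCKD as the only difference.
- **The primary inference is little affected.** Randomisation protects the comparison, planned content is equal by month 6, and the mismatch is largest at the secondary time points. All of this stands and limits the severity.

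**Conclusion.** The contradiction is real and should be corrected. Under Appendix 3 the VLCKD arm starts the lifestyle programme 12–13 weeks late and completes it in about half the time. The lifestyle contact deficit is 3 at week 10, 2 at week 16 and none at week 26, where only start date and pace differ. The week-10, week-16 and week-26 contrasts would then compare two valid strategies without isolating the addition of the VLCKD.

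This rests on reading BMI 27+ in Appendix 3 as the programme of Appendix 2, and on a month of 4 to 4.35 weeks. If the flowchart is what is delivered, there is no difference between arms and the error is confined to the appendix. The documents give no basis for the size or direction of an effect of the delay on weight loss.

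**What to change.** State one lifestyle schedule for each arm, and make section 2.4, section 4.8, the flowchart and Appendix 3 agree. There are two ways to do this.

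1. Give the VLCKD arm the same lifestyle schedule from week 0 and delete the second schedule from Appendix 3. This keeps the add-on question and is preferable. What is then added is the VLCKD programme including its own coaching, not the diet apart from contact time.
2. Keep both schedules, assign each to an arm by name, mark the flowchart's lifestyle row by arm, correct the account in section 2.4 of the 16 weeks after the diet, and restate the primary objective and the planned conclusion as a comparison of two strategies.

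Under either option, section 2.1 should name the comparator as NB plus the lifestyle programme, which the synopsis rationale and section 4.8 already imply.

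The cost is protocol wording and a flowchart change; option 1 also moves lifestyle contacts already planned for the VLCKD arm to earlier dates. Ethics committee review is needed if the sponsor classes the change as substantial under section 8.7. No extra patients or in-clinic visits are required, and the test and sample size do not change.
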